**Table 1. Study Protocol** 

Tubic 1. Study	1100001					
	Admission (0 hours)	2 hours post - placement	24 hrs.	Daily	5 days*	Discharge
Screening & Consent	X					

Demographics	X					
Neurostimulator (PENFS) vs sham	X	X	X	X	X	
Rome IV questionnaire 	X					
INVR (vomiting scale; daily during therapy) 	X	X	X	X	X	X
Abdominal pain (Visual Analogue Scale)	X	X	X	X	X	X
Need for opiates and other rescue medications	X	X	X	X	X	X
Length of stay						X
Patient Satisfaction Survey						X

INVR=Rhodes Index of Nausea, Vomiting & Retching; CGRP= Calcitonin Gene-Related Peptide

**Statistical Analysis:** Summary statistics, such as mean, median, standard deviation and range will be used as a first step to examine data. To satisfy parametric assumptions, we may perform transformations with justifications if possible and otherwise use non-parametric tests. For any binary outcomes, we will use Chi-square or Fisher's exact tests to compare the proportions between the two groups. We will compare the different variables (average daily reduction in abdominal pain, nausea/vomiting scores, average daily use/frequency/dosage of rescue medications (opiates, antiemetics and sedatives) between PENFS vs sham device. Data analyses will be performed using SAS version 9.4 (SAS institute, Cary, NC).

**Potential Pitfalls:** This pilot data is both safe and non-invasive and will help us better understand the pathophysiology underlying CVS symptoms. The proposed device is non-invasive and currently utilized at our institution. The PI is certified in the PENFS placement and has already used it in some of her patients with success. We thus expect no feasibility or safety issues. Potential risks generally would include bleeding or infection at the puncture site, pain at the application site, or skin irritation at the site of application.

**Feasibility**: Recruitment should not pose a problem as the PI ([name]) has the largest cohort of patients with CVS in the nation. Further in our experience, CVS sufferers are also highly motivated to enroll in studies and trial new therapies The PI also works closely with the Cyclic Vomiting Syndrome Association, who will advertise the study on their website and

\* questionnaires will be completed as an outpatient if patient is already discharged

through email and supports this project. Co-PI ([name]) and [name] have worked extensively with the PI and published collaboratively in the field. [name], the Section Chief, along with [name], both hospitalists, are aware and will oversee all the logistics regarding the admissions and the study, as CVS patients are typically admitted under Hospitalist service. In a recent neurostimulation trial conducted by [name], a high degree of compliance and a low dropout rate (12%) was observed despite a sham-controlled study design. Patient satisfaction with this non-pharmacological therapy was extremely high.

In summary, this proposal will evaluate a novel, safe and non-invasive therapy for a debilitating and prevalent disorder with few established treatment options. Demonstrating that this therapy is effective in treating and preventing CVS via neuromodulation will allow us to apply for extramural funding and expand our studies to a larger number of CVS patients and possibly other conditions.

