## (C) Approach, Feasibility, and Environment

## Aim 1: Investigate the efficacy of PENFS in adults admitted with cyclic vomiting syndrome

## Methods

**Inclusion/Exclusion Criteria.** We will enroll 80 adults between the ages of 18-65 years with a diagnosis of CVS (based on Rome IV diagnostic criteria). This study will only include patients who are admitted to Froedtert Hospital with an episode of CVS. Exclusion

criteria includes developmental delays, non-English speaking patients, pregnancy, any implanted electrical device or any significant dermatological/infectious condition of the ear.

Randomization. Subjects will be randomized to the intervention group (receiving the Bridge device) or control group (receiving an identical sham device lacking electrical charge) in 1:1 ratio. The auricular neurostimulator device will be placed on the subject's ear upon presentation to the hospital. The device delivers low voltage (3.2), continuous stimulation for 5 days (around the clock) in alternating frequencies (1-10Hz) with an impulse interval of 100ms/2 sec. The neurostimulators (for both treatment arms) will be placed by a certified MD/APP/RN inside the patient's room. All patients will be allowed to receive rescue medications after implantation of the device if the symptoms do not improve with the device or at patient's request.

We have performed a sample size calculation based on prior data. At a significance level of 0.05 and 80% power, we estimate a sample size of 40 participants per group to detect the minimum standardized effect size of 0.64 using two-sided tests, using prior data. We will compare the different variables (average daily reduction in abdominal pain, nausea/vomiting scores, average daily use/frequency/dosage of rescue medications (opiates, antiemetics and sedatives between PENFS vs sham device.

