Outcomes. Primary outcome will include the change in abdominal pain and concurrent opioid use. Abdominal pain will be assessed daily through Visual Analog Scale with the score ranging from 0 to 10, with 0 being the least and 10 being the worst pain. The need for opiates will be assessed through- (a) the time taken by the subject from the time of admission to the first felt need accompanied by the actual administration of opiates (IV hydromorphone or morphine), (b) daily frequency and total dosage of opiates received. Secondary outcomes will include- (a) severity of daily nausea and vomiting assessed through the Index for Nausea, Vomiting and Retching (INVR); (b) the need for other rescue medications (which include antiemetics like ondansetron, promethazine & metoclopramide; benzodiazepines like lorazepam; antihistaminics like diphenhydramine, etc.), (c) hospital LOS and (d) survey on patient satisfaction. While all other outcomes will be assessed daily, LOS and patient satisfaction will be assessed at the time of discharge (Table 1). All variables will be compared between the subjects in intervention arm versus control arm.

We hypothesize that PENFS will effectively mitigate the abdominal pain, nausea and vomiting associated with CVS episodes, obviate or reduce the need for opiates and simultaneously improve healthcare outcomes including LOS and patient satisfaction.

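### Pain is compared as a reduction with no baseline covariate named, although admission VAS is scheduled; prespecifying adjustment is a cheap precision gain, of uncertain size

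*Combined protocol and SAP*

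**What the plan says.** The Outcomes paragraph states: "Primary outcome will include the change in abdominal pain and concurrent opioid use". It adds: "Abdominal pain will be assessed daily through Visual Analog Scale", on a 0 to 10 scale. The Methods and the Statistical Analysis paragraph both say that the "average daily reduction in abdominal pain" will be compared between the two devices, along with nausea/vomiting scores and rescue medication use.

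For analysis tools, the plan lists summary statistics, transformation where parametric assumptions need it, non-parametric tests otherwise, and Chi-square or Fisher's exact tests for binary outcomes. It mentions no regression, covariance analysis, mixed model or covariate.

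Table 1 marks the VAS and the INVR at Admission (0 hours), 2 hours after placement, 24 hours, daily, 5 days and discharge. The footnote on outpatient completion is attached to the 5-day column only, and the INVR row limits daily collection to the therapy period.

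The sample size paragraph gives 40 per group at two-sided 0.05 and 80% power, to "detect the minimum standardized effect size of 0.64 using two-sided tests, using prior data". It does not say which outcome, or which SD, the 0.64 refers to.

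**The concern.** A change score subtracts the admission value in full, which fixes the coefficient on baseline at 1. A model with admission VAS as a covariate estimates that coefficient from the data. When the true slope differs from 1, the change score carries avoidable variance. In an 80-patient trial that can matter, and the covariate needed to remove it is already on the schedule.

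Timing matters too. An adjusted analysis is convincing as the primary one only if it is named before the data are seen.

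The point covers pain, which is one part of the primary outcome, and INVR. It does not bear on opioid use or length of stay.

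**Working it through.** **Inputs from the documents:** two-sided alpha 0.05, power 80%, standardized effect 0.64, 40 per group, 1:1 allocation.

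**Assumptions (not in the documents):** 0.64 is in SDs of the change score; correlation r between admission and follow-up VAS is 0.3 to 0.7; k = admission SD / follow-up SD is 0.5 to 1.0; one follow-up value.

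**Step 1: reproduce the plan's figure.** An ordinary two-sample t-test at 0.64 gives 79.7% power with 39 per arm and 80.7% with 40. The stated 40 is therefore reproduced without any adjustment.

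**Step 2: variance ratio.** With the follow-up SD set to 1:

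- Var(change) = 1 + k² − 2rk
- Var(adjusted) = 1 − r²
- VR = (1 − r²) / (1 + k² − 2rk)

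Adjusting the change score for baseline gives the same arm difference as adjusting the follow-up score, so VR applies whichever is the response. The baseline slope for follow-up is r/k. At r/k = 1, VR = 1 and nothing is gained.

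Example: r = 0.3, k = 1 gives VR = 0.91 / 1.40 = 0.65. The confidence interval is then about 19% narrower, since 1 − √0.65 = 0.194.

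**Step 3: power at 40 per arm.** Two-sided noncentral t with 2n − 3 = 77 degrees of freedom, and variance multiplied by 1 + 1/(2n − 4) = 1 + 1/76 for estimating the slope. The comparator is 80.7%.

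| k | r = 0.3 | r = 0.5 | r = 0.7 |
|---|---|---|---|
| 1.0 | 93.6% | 90.0% | 86.1% |
| 0.7 | 86.1% | 82.2% | 80.2% |
| 0.5 | 81.8% | 80.2% | 83.0% |

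Simulation (20,000 trials per setting) agrees. For r = 0.3, k = 1 it gave 80.6% unadjusted and 93.5% adjusted; for r = k = 0.7, 80.8% and 80.5%.

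**Step 4: worst case.** Apart from the cost of estimating one slope, the adjusted variance cannot exceed that of the change score. The worst case is a true slope of exactly 1, where power falls from 80.7% to 80.2%, a loss of 0.5 point. At 35 per arm (40 × 0.88 = 35.2, using the 12% dropout that the Feasibility paragraph reports from another trial), it falls from 75.2% to 74.5%.

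**Step 5: averaging several days.** For the mean of 5 daily values, let w be the correlation between follow-up days and Vf = (1 + 4w)/5. Then Var(change) = Vf + k² − 2rk and Var(adjusted) = Vf − r². With w = 0.8, adjusted power over the same grid is 80.2% to 95.1%. With w equal to r, it is 80.2% to 99.2%, but the top figure needs equal SDs and a day-to-day correlation of only 0.3.

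**Step 6: narrow admission pain.** The Special Emphasis section describes admission pain as typically intense, which suggests a small k. With k = 0.3 to 0.5, r = 0.3 to 0.5, w = 0.8 and 5 days, adjusted power is 80.2% to 82.7%: almost no gain.

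**The case against.** **Unadjusted is inferred from silence.** The plan names no test for continuous outcomes, and its reference to parametric assumptions would fit a linear model as well as a t-test. The match of 40 to a t-test is weak evidence, because trials are often sized that way and then analysed with covariates. This stands: the plan does not exclude adjustment. It does not commit to it either, and that commitment is what is missing.

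**The change comparison is sound.** A reader might infer that it is biased or that the sample size is wrong. Neither follows. Randomization makes the comparison unbiased with a valid standard error, and the 40 per group is reproduced.

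**The gain may be small.** This stands. A reader might take 99.2% power as the expected benefit, but nothing in the documents supports the inputs it needs, and Step 6 shows a plausible case with almost none.

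**The daily data may be uneven.** A reader might assume that five daily values exist for everyone, including at home. Table 1 does not establish this, because its outpatient footnote marks only the 5-day column. A mean over whatever values exist could then depend on length of stay, which is itself an outcome. For illustration, take assumed VAS values of 8, 6, 4, 2, 1 on days 1 to 5. A patient who stays averages 21/5 = 4.2. The same patient discharged after day 2, with a day-5 value, averages (8 + 6 + 1)/3 = 5.0. If the device shortens stay, such a rule would count against it. This stands and shapes the fix.

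**INVR may be compared as scores and not as reductions.** The wording allows that reading. The change-score criticism then would not apply to INVR, though adjusting for its admission value remains reasonable.

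**Conclusion.** The point holds as a free or cheap improvement of low severity. The plan names no baseline adjustment for pain although the baseline is scheduled. Under the assumptions listed in the working, with one follow-up value, adjustment moves power at 40 per arm from 80.7% to between 80.2% and 93.6%.

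The size cannot be narrowed from the documents. If 0.64 is instead in SDs of a single follow-up value, the change runs from −0.4 to +17 points over the same grid. Averaging several days may give more. Uniformly intense admission pain that is only weakly related to later pain would leave the gain near zero. The case for the change is the asymmetry: a ceiling of about half a point on the loss at the planned effect size, against a possible gain of several points or more.

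**What to change.** Keep the pain summary the plan already uses, define it as reduction from admission, and replace the two-group comparison with wording such as:

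> The primary pain analysis is a linear model of each patient's mean daily reduction in VAS from admission, with treatment arm and admission VAS (recorded before device placement) as covariates. The adjusted difference and its 95% CI will be reported. INVR will be analysed with admission INVR as covariate. The unadjusted comparison and a rank-based analysis are sensitivity analyses.

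The pre-placement condition needs stating because the device goes on the "ear upon presentation to the hospital" and Table 1 puts both device and VAS at 0 hours, without giving their order.

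If the number of daily values turns out to vary with length of stay, use a repeated-measures model with day, arm, arm-by-day and admission value in place of a raw mean over uneven days. The choice between the two should be written down before the data are seen. Do not adopt a mean-of-available-values rule, and do not assume that daily outpatient values are already scheduled.

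The cost of the linear model is a wording change, one degree of freedom per endpoint and at most about 0.5 percentage point of power at 40 per arm. It needs no further patients, visits or assessments; only the order of admission VAS and device placement has to be fixed. The repeated-measures version estimates more parameters, so the one-degree-of-freedom figure does not apply to it.

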## PROJECT TITLE:

Effectiveness of Electrical Neurostimulation as an Opioid-Sparing Alternative in the Treatment of Cyclic Vomiting Syndrome.

PI NAME	[name]	
CO-PI NAME(s)	[name]	
Co-Investigators	[name] [name]	

NCT#: NCT04721171

Document Date: 02/18/2019

Cyclic vomiting syndrome (CVS) is a chronic functional gastrointestinal disorder (FGID) characterized by episodic nausea, vomiting and severe abdominal pain in majority (80%) of patients. Most patients also have a migraine headache, photophobia, phonophobia and lethargy during an episode. The pathophysiology of CVS is not known but is thought to be a migraine diathesis given the overlap between the two syndromes. Various factors such as mitochondrial DNA polymorphisms, genetic variants in the cannabinoid receptor genes and and calcitonin gene-related peptide (CGRP) are thought to play key roles.

CVS is common and affects 2% of the population in the US. The disorder is disabling, and healthcare costs associated with CVS hospitalizations in adults are staggering, amounting to \$200 million dollars bi-annually. Due to sub-optimal therapies, hospitalized patients are usually treated empirically with IV fluids, anti-emetics, benzodiazepines and opioids for the intense abdominal pain. Unfortunately, opiate therapy in CVS is fraught with problems and is a risk factor for recurrent hospitalizations (preliminary data) as well as non-response to prophylactic therapy. Additionally, use of opioids is associated with dependence, withdrawal, addiction, overdose and even death. Hence, there is a critical need for safe, opiate-sparing strategies to treat pain associated with CVS episodes. Neurostimulation via a novel auricular percutaneous electrical nerve field stimulation (PENFS) device has recently emerged as a safe and non-invasive therapy for the treatment of pain, nausea and vomiting disorders. This therapy was recently FDA-approved for the symptoms of opioid withdrawal. Preliminary data indicates that PENFS modulates peripheral vagal nerve signaling, likely also modulating the trigeminal pathway from the external ear to the brainstem.

We hypothesize that 1) **PENFS** is a safe, non-invasive opioid-sparing alternative therapy for the severe abdominal pain, nausea and vomiting associated with CVS. We also hypothesize that 2) PENFS reduces length of stay (LOS), and improves patient satisfaction. We propose the following specific aim:

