# Aim 1. Investigate the efficacy of PENFS compared to a sham in hospitalized patients with CVS

## **Objective 1:**

- a. Demonstrate reduction in abdominal pain, nausea and vomiting using validated tools.
- b. Obviate or reduce the need for opioids.
- c. Reduce length of hospital stay and improve patient satisfaction.

This approach will specifically address the current opioid problem using a novel, non-invasive neurostimulation therapy with proven efficacy for opioid withdrawal. Long-term, it may improve health care outcomes and significantly reduce overall health care costs.

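### Hypothesis 1 calls the device safe, but no outcome, Table 1 row or analysis variable records adverse events or device-site reactions

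*Combined protocol and SAP*

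**What the plan says.** The project summary hypothesises that PENFS "is a safe, non-invasive opioid-sparing alternative therapy for the severe abdominal pain, nausea and vomiting associated with CVS". Safety is asserted again in the closing summary of section (C), in Special Emphasis and in the future plans under Project Timeline.

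The parts of the plan that define what is measured do not mention it:

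- Aim 1 is to "Investigate the efficacy of PENFS compared to a sham in hospitalized patients with CVS". Objectives a to c cover symptoms, opioid need, length of stay and satisfaction.
- Outcomes, in section (C): "Primary outcome will include the change in abdominal pain and concurrent opioid use". The secondary list opens with "severity of daily nausea and vomiting assessed through the Index for Nausea, Vomiting and Retching (INVR") and goes on to other rescue medication, length of stay and satisfaction, where it ends. The hypothesis restated after that list leaves safety out.
- Table 1 has rows for consent, demographics, device or sham, the Rome IV questionnaire, INVR, abdominal pain, rescue medication, length of stay and satisfaction.
- Statistical Analysis names pain, nausea and vomiting scores, and rescue medication.

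Potential Pitfalls says "We thus expect no feasibility or safety issues" and then lists the risks: "Potential risks generally would include bleeding or infection at the puncture site", followed by application-site pain and skin irritation.

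**The concern.** The plan states a hypothesis about safety and names the harms it would look for, but provides no place to record them. Followed as written, the trial could report no safety problems because none were asked about. The expectation of no problems rests on local use of the device and the investigator's own experience with some patients, not on data this trial would gather.

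The device breaks the skin at a puncture site and is to run continuously for 5 days, so site reactions are the obvious harms to count. The results are also meant to support a larger multicentre application, which would need event counts with denominators.

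**Working it through.** **Inputs from the plan.** 40 participants per group and 80 in total, 1:1 allocation, standardised effect 0.64, two-sided 0.05, 80% power (Methods); 12% dropout in an earlier neurostimulation trial (Feasibility). The plan gives no adverse-event rate, so every event rate below is an assumption.

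**1. The plan's own figure.** The normal approximation gives n = 2 × ((1.960 + 0.842) / 0.64)² = 38.3, so 39 per group. The two-sample t-test gives 39.3, so 40 per group, with power 80.7%. The stated 40 reproduces. It was sized for a mean difference and says nothing about safety.

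**2. Where safety could appear.**

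| Place | Safety item |
|---|---|
| Hypothesis 1 (project summary) | Yes, asserted |
| Aim 1 and objectives a to c | None |
| Primary and secondary outcomes | None |
| Table 1 rows | None |
| Analysis variables | None |
| Potential Pitfalls | Four risks named, with no definition, timing or analysis |

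**3. What zero events would exclude, if events were collected.** The exact two-sided 95% upper limit for 0 of n is 1 − 0.025^(1/n).

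- 40 active patients: 1 − 0.025^(1/40) = 8.8%.
- 35 active patients (40 × 0.88 = 35.2, if the 12% dropout applied): 1 − 0.025^(1/35) = 10.0%.
- 80 pooled: 1 − 0.025^(1/80) = 4.5%. This assumes that the sham also punctures the skin. Methods describes it as identical apart from the electrical charge, which suggests so without saying it.

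**4. Chance of seeing at least one event among 40 patients:** 1 − (1 − p)^40.

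| Assumed rate p | Chance |
|---|---|
| 1% | 33% |
| 2% | 55% |
| 5% | 87% |
| 10% | 98.5% |

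**5. Comparing arms at 40 per group** (normal approximation, two-sided 0.05, assumed rates). Power is 13% for 5% against 10%, 53% for 5% against 20%, and 85% for 5% against 30%. Only large differences would be detected, so a safety analysis should be descriptive.

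**The case against.** The strongest reply is that this is a pilot proposal whose aim is efficacy. Safe is one word in the summary hypothesis, the Methods restatement drops it, and the mismatch could be settled by deleting the word. That stands as a legitimate alternative remedy. It does not justify leaving both texts as they are.

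Second, adverse-event procedures may sit in IRB or consent papers outside these documents; the timeline has the IRB submission in progress. A reader might therefore infer too much in saying that the trial will end with no safety data at all. What the documents support is narrower: this plan schedules none and refers to no such procedure. The IRB consultation under CTSI Support is oversight, not data collection.

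Third, Table 1 has a device row marked from admission to day 5, which might be read as a device check. It is ambiguous, but it names no event or site finding. The general provision for testing binary outcomes does not help either, because no adverse event is named as an outcome. The pain scale is for abdominal pain.

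Two further stronger readings are tempting. One is that half of hypothesis 1 is untestable; the hypothesis joins safety with opioid-sparing efficacy and gives no basis for such a split. The other is that patients wear the device at home unchecked. The 5-day stimulation period and the footnote on outpatient questionnaires make wear after discharge plausible, but the plan does not state it.

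**Conclusion.** The concern holds for the safety component of hypothesis 1. As the plan is written, that component cannot be tested, and a statement that the device is safe would have no data behind it. The efficacy outcomes and the sample size are unaffected.

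No precision can be stated for data that are not scheduled. If events were collected for everyone, the best case of zero events would exclude true rates above 8.8% in the active arm, or above 4.5% pooled if the sham carries the same puncture risk. These limits assume full follow-up. The detection chances, from 33% to 98.5%, depend on assumed rates of 1% to 10% for which the plan gives no source. The change is worth making because it is cheap and would produce evidence on a claim the plan repeats several times.

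**What to change.** - **Table 1:** add one row, Adverse events and device-site reactions (bleeding, infection, pain, irritation, early removal), at the existing 2-hour, 24-hour, daily, day-5 and discharge contacts. For patients already discharged at day 5, use self-report on the outpatient questionnaire. The footnote provides for questionnaires only, so an ear inspection at that point would need an extra visit.
- **Outcomes:** list safety as a descriptive secondary outcome.
- **Statistical Analysis:** report counts per arm and, for site reactions, pooled counts as well, each with an exact 95% interval. State whether the sham punctures the skin. If it does, the between-arm contrast says little about puncture harm and the pooled count is the informative one.
- **Conclusion:** word it as event rates above x% were excluded, with x taken from the interval, and not as safe.
- **Alternative:** if safety data will not be collected, remove the claim of safety from hypothesis 1 and from the conclusions. If adverse-event procedures exist in the IRB papers, refer to them and still specify the by-arm summary.

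Cost: a few minutes per contact, one descriptive table, self-reported data after discharge, and a more modest safety statement.
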